6.1.2 DOSING AND ADMINISTRATION

Subjects will be monitored with the devices Airmod and Capnostream™35 simultaneously on Visit 2; both devices should be ready and apply correctly on the subject before sedation.

- Airmod administration procedure

Preparation

1. The device with Airmod should have enough battery life that last for the whole study process. Attach the device with Airmod with the AS-101 using type- C to type-C cable.
2. Place the auscultation sensor on the patient neck (left or right-side plain area of thyroid cartilage), secure with surgical tape.
3. Click on the 'Airmod' on the screen of the device to enter the software interface. When the device with Airmod and AS-101 are properly connected, an indicator light should come up, and then are able to click on the start/stop button to start monitoring.
4. By clicking the start/stop button, immediately breathing sound and spectrogram should be presented via speaker and display screen respectively, and if the signal or reception is unstable, adjust the auscultation sensor or secure with surgical tape to improve.

Monitoring (start time)

5. To start recording the monitoring for the study, on the display screen, select start/ stop button and entering the patient ID.

Monitoring (end time)

6. To end monitoring and terminate the saving process, on the display screen, select the start/stop button. This procedure should be done at the time point where the subject is ready to discharge from post anesthesia care unit (PACU) or the end of non-anesthesia period, which compliance with the criteria PAR or PADSS score ≥ 9 or determined termination by principal investigator.

- Capnostream™35 administration procedure

Preparation

1. Capnostream™35 should have enough battery life that last for the whole study process.
2. To set up for the subject, on the monitoring display screen, select menu -> action -> patient admin -> insert the subject number.
3. Connect the sampling line to the monitor, rotate it clockwise until it can no longer be turned; and also connect the sampling line to the subject nostril, adjust the tightness at the lower band to fit on the subject. When properly connected, the monitor will immediately begin to search breaths, then present EtCO_2 value and waveform on the display screen after 3.4 ~ 5.0 second.

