9.4.2 ANALYSIS OF THE PRIMARY EFFICACY ENDPOINT(S)

In this study, all the measurements were conducted in the same subject, and the clocking variance would be limited by investigator justification procedure to acquire the utmost matching recording. The study design is a paired non-inferiority test to evaluate accuracy and performance of respiratory rate (RR) measurement from Airmod compared to Capnostream™35. The primary objective is to establish the non-inferiority. The primary end goal is to test the entire effect at the margin of 3 breaths per minute (bpm). The non-inferiority is a directional (one-sided) test. The null hypothesis (H0) and alternative (H1) are defined as:

$$\begin{aligned} H_0: \mu_{\text{AirRR}} - \mu_{\text{ManCRR}} &< -3; \\ H_1: \mu_{\text{AirRR}} - \mu_{\text{ManCRR}} &\geq -3. \end{aligned}$$

At the interim analysis, under 99.69% CI, when reject the null hypothesis (H0) indicates the non-inferiority.

At the final analysis, under 95.1% CI, when reject the null hypothesis (H0) indicates the non-inferiority.

A subgroup analysis for those subjects with $\text{BMI} \geq 30$ will follow the original study design in a stratified sample pool to test the non-inferiority at the margin of 3 bpm.

According to 7.2, part of the measurement result within subject will be censored and excluded in the paired non-inferiority test. The principle of exclusion is based on the investigator reported failure event/period of Airmod or Capnostream™35, the report will be confirmed by the principal investigator. The data prior to discontinuation or following a fixed machine failure period will be included in the paired non-inferiority test.

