Bland-Altman analysis is used to measure the consistency of continuous data from two distinct measurements. Therefore, the likelihood of AirRR and ManCRR will be quantified and visualized on the assumption of fixed observer and pairs Bland-Altman analysis. It combines the quantitative analysis of LoA (limits of agreement) and the qualitative analysis of scatter plot to show an instinctive evaluation between two methods of their correlation. Each of the n samples is then represented on the graph by assigning the mean of the two measurements as the x-value, and the difference between the two values as the y-value. By this graphical method, we can extend a simple logarithmic transformation approach to data where there is a relationship between difference and magnitude. We discuss the importance of repeatability of RR measurements from each equipment and compare an estimate of this to the LoA. [20] In this case, if the difference of RR measured from two equipment are in the 95% LoA, we will say that RR measured from these two equipment are correlated and acceptable.

$$S(x, y) = \left(\frac{\Delta G_A + \Delta G_E}{2}, \Delta G_A - \Delta G_E \right)$$

3. Use paired t-test to compare the response time of Airmod versus Capnography on Capnostream™35 after administration of jaw thrust. In the target of $p<0.05$ indicates significance. The principal investigator and research members will determine the apnea period and the first effective breath.

The paired t test can be used when the two groups under comparison are dependent on each other. [21] By acquiring the T value from paired t-test, we can obtain the p value indicating the significant difference level via t-distribution table or Microsoft Excel. A p value less than 0.05 would indicate that Airmod is able to resume RR estimation after proper intervention faster than Capnostream™35.

$$t = \frac{\bar{X}_1 - \bar{X}_2}{\sqrt{\frac{(s_1^2 + s_2^2)2\rho s_1 s_2}{n}}}$$

4. Capnography is inherently limited in certain circumstances which may cause ineffectively detecting CO₂, including movement, nasal cannula drop, blocked, or other situations. Airmod is superior to capnography in these limitations since it detects and measure breath sound directly.

4.1 The difference of ManCRR minus AirRR and ManCRR minus CapRR indicates non-inferiority at margin of 3 bpm (M1) and sampling rate 1Hz.

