the actual measurement of the respiratory event.

9.2.2 Analysis to measure the agreement between AirRR and ManCRR.

Bland Altman analysis, and concordance correlation is adopted to measure the agreement between AirRR and ManCRR. The quantitative results of respiratory rate from these devices under test over time are evaluated by the above mentioned method to analyze the mean and bias from the plot and concordance correlation coefficient.

Fig 9. Bland Altman between AirRR and ManCRR (Example)

Fig 10. Correlation between AirRR and ManCRR (Example)

Fig 11. Correlation between AirRR and ManCRR during induction period (Example)

Evaluating the Non-Inferiority of Airmod to Capnostream™35 on Respiratory Rate Monitoring and User Experience Clinical Evaluation

Fig 12. Correlation between AirRR and ManCRR during Inter-operation period (Example)

Fig 13. Correlation between AirRR and ManCRR during transportation and PACU period (Example)

Also, we apply a sensitivity test for Airmod by comparing the reference method at each time point and calculating the absolute deviations in breaths per minute (bpm). As a measure of accuracy, absolute deviations were calculated as a percent of reference.

Percent absolute deviation were averaged for each subject yielding overall measures of accuracy. To evaluate the accuracy of Airmod, the individual percent absolute deviation was compared for each monitoring time point by subtracting ManCRR from AirRR and then averaged within subject. A paired t test was used to evaluate significance across subjects.

To measure the precision of Airmod for each subject, the standard deviation of percent deviations (in nonabsolute value) was calculated. The precision of Airmod was compared through a paired t test of the subject-specific standard deviations of Airmod's percent deviations from reference.

9.2.3 Analysis to evaluate the response time of the first breath detection followed by administration of jaw thrust during the apnea period. The 3rd secondary objective is to compare the response time of Airmod versus Capnography.

Use paired t-test to compare the response time of Airmod versus Capnography on Capnostream[™]35 after administration of jaw thrust. The target of p<0.05 indicates significance difference.

Evaluating the Non-Inferiority of Airmod to Capnostream™35 on Respiratory Rate Monitoring and User Experience Clinical Evaluation

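### The response-time endpoint declares Airmod faster on p<0.05 alone, with no sidedness, order of subtraction or sign condition, and the SAP draws only a difference from the same p value

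*Protocol*

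**What the plan says.** Protocol 9.4.3 item 3 sets the test: "Use paired t-test to compare the response time of Airmod versus Capnography on Capnostream™35 after administration of jaw thrust". The threshold follows: "In the target of $p<0.05$ indicates significance". The p value is obtained from the t statistic: "we can obtain the p value indicating the significant difference level via t-distribution table or Microsoft Excel". The protocol then gives the conclusion to be drawn: "A p value less than 0.05 would indicate that Airmod is able to resume RR estimation after proper intervention faster than" Capnostream 35.

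The printed t statistic has a signed numerator, the mean of X1 minus the mean of X2, but the text does not say which device is X1.

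SAP 9.2.3 repeats the paired t-test and stops at a weaker conclusion: "The target of p<0.05 indicates significance difference". It gives no direction and no sidedness either. The endpoint lists in the protocol synopsis, Protocol section 3 and SAP 4.4 mention only p<0.05 and significance.

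For the primary comparison, by contrast, Protocol 9.4.2 does specify direction: "The non-inferiority is a directional (one-sided) test".

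**The concern.** A p value from a two-sided test measures evidence against equality. It carries no direction. Direction comes from the sign of the estimate or from a one-sided alternative fixed in advance, and the response-time rule has neither. As worded, it attaches a favourable comparative conclusion to any sufficiently small p value, including one produced by Airmod being slower.

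The two documents also disagree about what a significant result means. The protocol would report a speed advantage over a marketed device, whereas the SAP would report that the two times differ. The endpoint is secondary, but a statement that one monitor recovers faster than another is the kind that gets quoted, so the rule behind it should be unambiguous.

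**Working it through.** **No figure to reproduce.** Neither document gives a number of jaw-thrust events, an expected difference, an SD or a power for response time. The check therefore shows how the written rule behaves over assumed values.

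**Inputs from the documents.** Paired t-test and a 0.05 threshold (Protocol 9.4.3 item 3, SAP 9.2.3). The conclusion of faster at p<0.05 comes from Protocol 9.4.3 item 3 only.

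**Assumptions.** Let D be Airmod minus capnography response time, so a positive D means Airmod is slower. Let d be the true mean of D divided by the SD of D. The pairs are independent, n is 20, 30 or 50, and d is 0, 0.2 or 0.5. A mean of 2 s with an SD of 4 s, for example, gives d = 2/4 = 0.5.

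**Three rules.**
- L (literal, two-sided): faster whenever |t| > t(0.975, n−1).
- S (two-sided with sign condition): faster only if t < −t(0.975, n−1). This is the same as the whole two-sided 95% CI for the mean of D lying below zero.
- O (one-sided 0.05 in Airmod's direction): faster only if t < −t(0.95, n−1).

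**Formula.** t follows a noncentral t distribution with n−1 degrees of freedom and noncentrality d√n. For n = 30, t(0.975, 29) = 2.045.
- d = 0.5: noncentrality 0.5 × √30 = 2.739. P(t > 2.045) = 0.754, and P(t < −2.045) is below 0.0001. Rule L gives 0.754.
- d = 0.2: noncentrality 0.2 × √30 = 1.095. P(t > 2.045) = 0.184 and P(t < −2.045) = 0.001. Rule L gives 0.185.

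**Probability of concluding faster when Airmod is equal or truly slower:**

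| n | d (Airmod slower) | L | S | O |
|---|---|---|---|---|
| any of the three | 0 | 0.050 | 0.025 | 0.050 |
| 20 | 0.2 | 0.136 | 0.002 | 0.006 |
| 20 | 0.5 | 0.564 | <0.0001 | 0.0001 |
| 30 | 0.2 | 0.185 | 0.001 | 0.003 |
| 30 | 0.5 | 0.754 | <0.0001 | <0.0001 |
| 50 | 0.2 | 0.284 | 0.0004 | 0.001 |
| 50 | 0.5 | 0.934 | <0.0001 | <0.0001 |

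With no true difference, rule L rejects 5% of the time, and in half of those cases (2.5 percentage points) Airmod is observed to be slower. With Airmod truly slower, the chance of the wrong conclusion under rule L rises with n, so more data make it worse. Under S or O it is small and falls with n.

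**The case against.** **Sidedness is unstated, so the fault may not exist.** If the sponsor intends a one-sided test in Airmod's direction, a slower Airmod cannot pass. This is correct, and two-sided is an inference. It is the more natural reading, because the p value is described in terms of difference and because the protocol labels its primary test as one-sided but not this one. The wrong-sign result is therefore conditional on a two-sided test. The missing specification is not conditional: under either reading the plan must state the sidedness and the order of subtraction.

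**A competent analyst would see the sign, and the SAP governs the detail.** The t statistic is signed, Protocol 9.4 refers details to the SAP, and the SAP claims only a difference. This limits the practical risk. It does not remove the protocol sentence, and a prespecified rule should not depend on someone overriding its wording.

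**The endpoint is secondary and has no stated power.** True. That bears on the weight of the point, not on its correctness.

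**A stronger reading that the documents do not support.** A reader might infer that the device clocks are shifted until breaths coincide, since Protocol 9.1 and 9.4.2 say "the clocking variance would be limited by investigator justification procedure to acquire the utmost matching recording", and that this could create or erase a delay of a few seconds. The sentence is unclear, sits in the primary-analysis text, and can equally mean recordings acquired at the same time. Protocol 8.1 supports that sense by requiring both devices to start and end together. Neither document describes shifting records or applies the sentence to response time. Part of SAP 9.1 and the response-time figure are also absent from the text available, so a missing synchronisation method cannot be asserted.

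The Capnostream preparation step in Protocol 6.1.2, "value and waveform on the display screen after 3.4 ~ 5.0 second", does not give the size of such an effect. It is a delay on first connection, and the same range is given there for the pulse oximetry line. Nor is there a basis for saying that agreement between AirRR and ManCRR is inflated: nothing establishes the shifting, and SAP 9.1 works with per-minute means.

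**Conclusion.** The decision rule in Protocol 9.4.3 item 3 is wrong as written. It equates p<0.05 with Airmod being faster without sidedness, order of subtraction or a sign condition, and it conflicts with SAP 9.2.3, which draws only a difference.

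Taken literally with a two-sided paired t-test, a true disadvantage of 0.2 to 0.5 SD would be reported as faster with probability of about 0.19 to 0.75 at n = 30. At 0.5 SD the range is 0.56 to 0.93 for n from 20 to 50. These figures rest on assumed n and standardised differences, independent pairs and the two-sided reading. They show how the rule behaves and do not predict this trial's result.

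The conclusion is confined to direction. It makes no claim about clock alignment or about agreement between the devices.

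**What to change.** In Protocol 9.4.3 item 3 and SAP 9.2.3, use the same text to:
1. Define the paired difference as Airmod response time minus capnography response time.
2. State the sidedness. A two-sided 95% CI is suggested. If a one-sided 0.05 test was intended, say so explicitly, because with no true difference its chance of concluding faster is 0.050 rather than 0.025.
3. Conclude that Airmod is faster only if the whole two-sided 95% CI for the mean difference lies below zero. If the whole interval lies above zero, report Airmod as slower. If it includes zero, claim neither.
4. Report the mean difference in seconds with its CI alongside the p value.

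Bring the short endpoint statements in the protocol synopsis, Protocol section 3 and SAP 4.4 into line.

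The cost is a few sentences in each document. Data collection and the paired t-test itself do not change. Compared with a one-sided 0.05 test, the CI rule asks for somewhat stronger evidence before faster is claimed.

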2.2 BACKGROUND

Sedation is commonly prescribed to reduce the patient's anxiety, discomfort and pain during certain procedures. All sedatives suppress the central nervous system in a dose-dependent manner, usually accompanied by a reduction in CO₂ responsiveness in the medullary respiratory center. One of the most common adverse effect associated with sedation is respiratory depression, and the greater the degree of sedation, the greater the degree of respiratory depression observed [12].

Monitoring of sedation is of great importance, not only avoid inadequate or over sedation, also assuring quality care and minimizing risk of adverse events [8, 13]. Given that capnography is the most reliable method to confirm airway device placement and monitor ventilation, as the current gold standard method [9, 14]. After initial placement, loss of the waveform can indicate movement of the tube, possible esophageal placement or circuit disconnection, which provides a continuous assurance of functional tube placement. In a 2001 study of 345 intubations, capnography had a sensitivity and specificity of 100% for correct placement [15].

The capnography waveform represents air movement in the lungs, starts at the beginning of exhalation, and senses air from dead space in the upper airway and bronchi. As carbon dioxide (CO₂) is a product of metabolism transported via perfusion and expelled through ventilation, the End-tidal carbon dioxide (EtCO₂) waveform adds an objective measurement on counting the respiratory rate (RR), where it increases as CO₂ rises, and decreases as CO₂ falls [16]. This provided real-time feedback on the patient's conditions, indicating the response to a treatment, where plans can be quickly adjusted when capnography is used to monitor trends.

The importance of monitoring respiratory rate as a key vital sign has been well defined in medicine [17]. An abrupt alteration in respiratory rate can help detect changes in the status of a patient during a crucial period where modifications in management might be needed. Respiratory monitoring is important for both patients receiving general anesthesia as well as for those who require sedation [17].

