	
coefficient, and on their mean and bias by Bland-Altman analysis.
 
[Time Frame: Non-Anesthesia Stage: Up to 40 patients will be randomly assigned to non-anesthesia stage assessment, the measurement will be evaluated after enrollment with ICF, at the NOR area. (5~30 minutes) Procedure Stage: From firstly anesthetic administration to end of procedure. (Depends on procedure 10mins ~ few hours) NORA stage : From transportation of subjects to PACU to discharge from PACU (PAR or PADSS score ≥ 9) (At least 15 minutes)] The information of patient monitoring period refers to 10.2.1.
	
distinct measurements. Therefore, the likelihood of AirRR and ManCRR will be quantified and visualized on the assumption of fixed observer and pairs Bland-Altman analysis. Further information refers to 10.2.6.

To evaluate the response time of the first breath detection followed by administration of jaw thrust during the apnea period. The 3rd secondary objective is to compare the response time of Airmod versus Capnography.
	
Use paired t-test to compare the response time of Airmod versus Capnography on Capnostream™35 after administration of jaw thrust. In the target of $p < 0.05$ indicates significance.
	
The principal investigator and research members will determine the apnea period and the first effective breath.

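### Protocol 9.4.3 concludes that Airmod resumes RR estimation faster, but the endpoint times first-breath detection and no sidedness is stated; the printed t formula also needs a check

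*Protocol*

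**What the plan says.** - **Objective.** Secondary objective 3 (Protocol 3; repeated in SAP 4.3 and 9.2.3) is "To evaluate the response time of the first breath detection followed by administration of jaw thrust during the apnea period", comparing Airmod with capnography.
- **Test.** Protocol 9.4.3 item 3: "Use paired t-test to compare the response time of Airmod versus Capnography on Capnostream™35 after administration of jaw thrust". The criterion is "In the target of $p<0.05$ indicates significance". One-sided or two-sided is not stated.
- **Event.** The same item has the investigator and research team determine the apnea period and the first effective breath.
- **p value.** After T is obtained, "we can obtain the p value indicating the significant difference level via t-distribution table or Microsoft Excel".
- **Conclusion.** A p value below 0.05 is taken to mean that Airmod is "able to resume RR estimation after proper intervention" faster than Capnostream 35.
- **Formula.** The displayed t statistic has, under the root and over n, the expression "s_1^2 + s_2^2)2\rho s_1 s_2". No operator stands before the term with rho.
- **SAP 9.2.3.** It names the same paired t-test, gives no formula, and says only that p below 0.05 marks a significant difference. It mentions neither direction nor resumption of RR estimation.

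**The concern.** The protocol's conclusion names a different quantity from the one measured, and it states a direction that the criterion does not contain. This is a comparative statement against a marketed monitor, so it governs what the trial may say from this endpoint even if the test is computed perfectly.

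The formula is a separate, smaller matter. The variance of a within-pair difference is s1² + s2² − 2·rho·s1·s2. The expression as read shows no minus, and by ordinary convention two adjacent factors are multiplied. If someone calculated T by hand from that expression, the result would not be a paired t statistic.

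**Working it through.** **Step 1. What is timed and what is claimed.**

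| | Detected breath | Respiratory rate |
|---|---|---|
| Form of output | Inhalation events with start and end times (SAP 9.2.1, Fig 7) | Rate in breaths per minute at 1 Hz (SAP section 9; rrUI in the SAP amendment table) |
| Named in objective 3 | Yes | No |
| Named in the Protocol 9.4.3 conclusion | No | Yes |
| Named in the SAP 9.2.3 conclusion | No; a difference only | No |

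SAP 7.4 adds that the interface shows NA or dashes when no estimate is available. Detecting one breath and displaying a rate again are therefore distinct, and a difference in the first does not establish a difference in the second.

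**Step 2. Direction.** The documents give no SD, correlation, expected difference or number of jaw-thrust events for this endpoint, so there is no stated figure to reproduce. Assumed for illustration: |d| = 2 s, s1 = 4 s, s2 = 5 s, n = 30.

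Standard form: t = d / sqrt((s1² + s2² − 2·rho·s1·s2)/n).

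- At rho = 0.5: (16 + 25 − 20)/30 = 0.70, root 0.837, so t = −2.39 if d = −2 s and +2.39 if d = +2 s. The two-sided p is 0.024 in both cases. The p value alone does not say which device was faster.
- At rho = 0.2: (16 + 25 − 8)/30 = 1.10, root 1.049, |t| = 1.91. The two-sided p is 0.066; the one-sided p in the favourable direction is half of that, 0.033. Sidedness decides whether the 0.05 target is met.

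**Step 3. The formula, if read as a product.** Then t = d / sqrt((s1² + s2²)·2·rho·s1·s2/n). The term under the root is in time to the fourth power, so t is in 1/time.

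At rho = 0.5 and d = −2 s: 41 × 20/30 = 27.33, root 5.228, t = −0.38 in seconds.

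| rho | Standard form, any time unit | Product, seconds | Product, minutes | Product, milliseconds |
|---|---|---|---|---|
| −0.2 | −1.56 | undefined | undefined | undefined |
| 0 | −1.71 | undefined | undefined | undefined |
| 0.2 | −1.91 | −0.60 | −36.29 | −0.0006 |
| 0.5 | −2.39 | −0.38 | −22.95 | −0.0004 |
| 0.8 | −3.65 | −0.30 | −18.15 | −0.0003 |

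On one simulated sample of 30 pairs, the standard form equalled a library paired t-test (−2.102 in both), while the product form gave −0.311. A product is therefore not a paired t statistic. Whether the plan contains one is a different question.

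**The case against.** **A reader might infer that the plan multiplies the covariance term and will produce an arbitrary p value.** The documents do not support that. The text was machine-read, and one lost minus sign gives exactly the string quoted. Equation content is missing close by: in the same section the MAPE heading has no formula under it. On the other side, minus signs survive in the numerator of this equation and in the Bland-Altman expression above it, and the brackets round s1² + s2² are needed only for a product. Neither observation is proof.

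Even if the source page has the error, the specified method is the named test: "By acquiring the T value from paired t-test, we can obtain the p value". SAP 9.2.3 repeats the test without any formula, and a standard routine does not use the printed display. Hand calculation is not ruled out, but nothing shows that it is planned. The formula is thus something to verify.

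**A reader might also infer that breath phase invalidates the comparison.** Airmod detects inhalation (Protocol 6.1.1), while the capnography waveform "starts at the beginning of exhalation" (Protocol 2.2), so part of an Airmod lead may be phase. But the endpoint is each device's response time, and an earlier signal is part of that. The plan does not claim to isolate processing speed, and the SAP figure illustrating the timing (Fig 14) is not visible. This is at most a caveat for interpretation.

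**The conclusion is one protocol sentence that the SAP does not repeat.** That is true, and it makes the fix short. The sentence still stands in the protocol as the reading of a significant result.

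**Conclusion.** The mismatch between endpoint and conclusion holds however the formula was printed. A significant result could support a statement about time to first-breath detection. It would not show that Airmod resumes RR estimation sooner, and without a stated sidedness or the sign of the mean difference it would not show direction. The consequence is an over-reaching comparative claim on a secondary endpoint; the primary analysis is untouched.

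The formula is unconfirmed. If the minus is truly absent it should be corrected, but the practical effect is small provided a standard paired t-test routine is used. The t values in the working rest on assumed SDs, correlation, difference and number of pairs. They show how each form behaves and do not predict the trial's result.

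**What to change.** 1. In Protocol 9.4.3 item 3, replace the conclusion so that it concerns time to first-breath detection after jaw thrust and no longer RR estimation.
2. In Protocol 9.4.3 and SAP 9.2.3, state the sidedness and define the paired difference as Airmod minus capnography. Allow the word *faster* only if the test meets its stated level and the mean difference is negative.
3. Check the t formula on the source page. If the minus is absent, print t = (mean 1 − mean 2) / sqrt((s1² + s2² − 2·rho·s1·s2)/n), or define t on the SD of the within-pair differences.
4. Add a time to RR recovery only if the stored 1 Hz outputs of both devices are first shown to go to NA during apnea. SAP 7.4 describes NA as out of detecting range or self-calibration; nothing says that RR becomes NA in an apnea, and SAP 10.1 lists apneas as short as 15 to 30 seconds. If RR never goes to NA, the variable is undefined.

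Items 1 to 3 cost a few lines of text and one look at the source page, with no new data. Item 4 is optional and depends on that check of the logs.
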